13.2.10. Safety

Adverse events in the ITT will be presented in summary tables and supporting data listings.

13.2.11. Health outcomes analyses

No specific health outcomes' analyses were planned in the protocol, except for those considered in the secondary objectives.

13.2.12. Changes to planned analysis

Any deviation(s) from the original statistical plan will be described and justified in the final report.

14. Ethics

14.1. Statement(s) of Compliance

- The study will be conducted in accordance with the protocol and ethical principles that have their origin in the Declaration of Helsinki (2003), the International Conference on Harmonization Guidelines on Good Clinical Practice, India GCP.
- The study will not begin until an IRB/EC approval as required are received.
- Any special requirements imposed by an IRB/EC will be followed for the respective sites.
- Since this is a post market study with follow up visits per the standard of care no additional compensation will be provided to subjects for the respective follow-up visits .
- Medtronic maintains appropriate clinical trial liability insurance coverage as required under applicable laws and regulations and will comply with applicable local law and custom concerning specific insurance coverage. If required a Clinical Trial insurance statement/certificate will be provided to the Medical Institution and Ethics Committee.
- The Name(s), title(s), address(es), and contact numbers of the investigator(s) who are responsible for conducting the study, along with their consent letter(s) (Investigator Statement), will be listed and kept separate from the CIP and will be updated by the sponsor.
- The Name(s), address(es) and contact numbers of the institution(s) particulars of the head(s) of the institution(s), will be kept separate from the CIP. The sponsor will maintain an updated list.
- If any action is taken by a IEC/IRB with respect to the investigation, that information should be forwarded to the sponsor.
- Warranty information is provided in the product packaging for the commercially released devices.

15. Study Administration

15.1. Monitoring

Monitoring visits will be conducted in accordance with Medtronic SOPs and the Monitoring Plan.

Frequency of monitoring visits may be based on subject enrollment, duration of the study and study compliance.

During the monitoring visit, it will be verified whether signed and dated Informed consent Forms have been obtained from each subject before any clinical-study-related procedures are undertaken.

Regulatory documents (e.g. EC approval letters and Clinical Trial Agreements) will be reviewed at each study center. Subject data will be monitored against source documentation (e.g. clinic and hospital charts). Center study progress, investigator's adherence to the CIP and maintenance of records and reports will also be checked.

The principal investigator(s), his/her delegate(s) and the study coordinator(s) shall be accessible to Medtronic field personnel, study monitors and the Clinical Study Manager. This accessibility is of particular importance for reviewing data in the eCRF. Direct access to patient medical files for source data verification will need to be granted and prepared prior to any monitoring visits. Subject compliance to the study and visits will be monitored periodically and all efforts to contact the patient telephonically and ensure availability for the visit will be done by the site team.

15.2. Data Management

The investigator must ensure accuracy, completeness and timeliness of the data reported in the eCRFs and in all other required reports. Data reported on the eCRFs which are derived from source documents and worksheets must be consistent with the source documents and worksheets as well. All discrepancies need to be justified in a documented rationale, signed and dated by the (principal) investigator and filed in the patient medical file.

Only authorized persons can complete eCRFs. eCRFs shall be signed by investigators (physicians only) as specified on the Delegated Tasks List included in the Investigator Site File.

The Electronic Data Capture (EDC) system maintains an audit trail on entries, changes or corrections in eCRFs. If a person is only authorized to complete eCRFs or make changes to an already signed eCRF, the investigator shall re-sign this eCRF.

A copy of the electronic Case Report Forms will be provided under a separate cover.

It is recommended that eCRF will be updated as soon as possible from the date the visit is completed. A delayed completion of the eCRF will not be considered a Protocol Deviation.

Data management will be done according to Medtronic SOPs and the Data Management Plan for this study. These documents will be made available on request.

All collected data will be reviewed for completeness, correctness and consistency. In case of issues, queries will be sent to the investigator to complete, correct or comment the data.

15.3. Direct Access to Source Data/Documents

In addition to regular monitoring visits, Medtronic may conduct audits at participating investigation sites. The purpose of an audit is to verify the adequate performance of the clinical study related activities. Independent of the employees involved in the clinical study. Regulatory authorities may also perform inspections at participating investigation sites. Any regulatory authority inspection announcements shall be forwarded immediately to Clinical Study Team.

The investigator and/or institution shall permit Medtronic and regulatory bodies direct access to source data and documents, taking into account any restrictions due to local law, to perform clinical study-related monitoring, audits, IEC review (if applicable), and regulatory inspections.

15.4. Confidentiality

All records and other information about subjects participating in this study will be treated as confidential.

Subject confidentiality will be maintained throughout the clinical study in a way that ensures the information can always be tracked back to the source data. For this purpose, a unique subject identification code (e.g. site number, subject number and subject initials) will be assigned and used to allow identification of all data reported for each subject.

Study data may be made available to third parties, e.g. in the case of an audit performed by regulatory authorities, provided the data are treated confidentially and that the subject's privacy is guaranteed. The identity of a subject will never be disclosed in the event that study data are published. Sites will maintain subject privacy according to local and national regulations and institutional requirements.

15.5. Liability

The India Medtronic Pvt Ltd is wholly owned subsidiary of Medtronic Inc., which as the parent company of such entity maintains appropriate clinical study liability insurance coverage as required under applicable laws and regulations and will comply with applicable law and custom concerning specific insurance coverage. If required, a Clinical Trial Insurance statement/certificate will be provided to the IEC.

15.6. CIP Amendments

In case the investigator proposes any appropriate modification(s) of the CIP or investigational device or investigational device use, Medtronic will review this and decides whether the modification(s) will be implemented.

Medtronic will submit any significant amendment to the Clinical Investigation Plan, including a justification for this amendment, to the appropriate regulatory authorities and to the investigators to obtain approval from their IEC, if applicable. Administrative amendments to the CIP will be submitted to the IEC and appropriate regulatory authorities for notification, if applicable.

15.7. Record Retention

At a minimum, the following records must be kept by the investigator:

- CIP and, if applicable, any amendments;
- instructions For Use;
- Medtronic and IEC approved Informed consent form (ICF);
- fully signed clinical investigation agreement and confidentiality agreement (if not included in the clinical investigation agreement);
- insurance certificates;
- completed Delegated Task List and Curriculum Vitae of all investigation site team members;
- training documentation of all site study members;
- relevant communications;
- subject identification;
- enrollment log;
- signed, dated and fully executed Informed consent Forms;
- fully executed eCRFs and corrections;
- interim and Final report;
- EC notification, correspondence and approval;
- EC membership list;
- statistical analyses;
- all essential correspondence concerning the clinical study between Medtronic and the clinical site;
- any other records as required by local requirements.

15.8. Publication and Use of Information

A detailed description of the Publication Policy will be described in the Publication Plan.

The Medtronic study team will collaborate to publish the results of the study in an appropriate/highest impact local (Indian) and global publications.

Publications and presentations referring to the MANDATE Study will be coordinated by Medtronic to allow the use of all available data. The following publication policy will have to be adhered to by all participating Investigational Centers:

Authorship on any publication(s) resulting from this study will be assigned according to substantial contributions to conception and design, acquisition of data, or analysis and interpretation of data, drafting the article or revising it critically for important intellectual content and final approval of the version to be published. This is in accordance with the Vancouver principles (The Uniform Requirements for Manuscripts Submitted to Biomedical Journals: Writing and Editing for Biomedical Publication, ICMJE, October 2008), as agreed upon by the editors of all major medical journals.

The number of authors will be dependent on the regulations of the concerning journal. Names of all participating investigators will appear in the Acknowledgment of the paper.

Based on the principle that Medtronic owns the data of the MANDATE study, a single Investigational Center may access and use the data provided by itself for scientific publications following prior approval by Medtronic.

Medtronic as the owner of the data can use the data and/or any results derived from the data or publications based on that data for marketing purposes, further research and development of devices or educational use.

The study sponsor will collect data in such way that no subject can be identified and monitor study records.

Participating subjects will not be identified by name in any published reports about the study. The study will be recorded on www.clinicaltrials.gov and www.CTRI.in before the first enrollment.

15.9. Suspension or Early Termination

Medtronic or Regulatory Authority may decide to suspend or prematurely terminate the study (e.g. if information becomes available that the risk to study subject is higher than initially indicated or because interim analysis indicates that the results significantly differ from the study objectives or statistical endpoints). If the study is terminated prematurely or suspended, Medtronic shall promptly inform the clinical investigators of the termination or suspension and the reason(s) for this. The investigator shall then promptly inform the reviewing IEC and the study subjects. The clinical research agreement will be amended or terminated.

15.9.1. Early investigation site suspension or termination

Medtronic, IEC or Regulatory Authority may decide to suspend or prematurely terminate an investigation site (e.g. in case of expiring approval of the reviewing IEC, non-compliance to the CIP or lack of enrollment). If an investigation site is suspended or prematurely terminated, Medtronic shall promptly inform the investigator(s) of the termination or suspension and the reason(s) for this. The investigator shall then promptly inform the reviewing IEC, if required, the study subjects and their general practitioner. When the risks are found to outweigh the potential benefits or when there is conclusive proof of definite outcomes, investigators must assess whether to continue, modify or immediately stop the clinical study in the respective investigation site and immediately inform the sponsor and reviewing IEC, if applicable.

1.0	
'Not Applicable, New Document'	[name] Clinical Study Manager

MANDATE AF Study Clinical Investigation Plan

Version [1.0, 26 Feb 2019]

Page 57 of 57

Medtronic Controlled Information

This document is electronically controlled

056-F275, v A Clinical Investigation Plan Template

## 1. Version History

Version	Date	Summary of Changes	Author(s)/Title
1.0	27-AUG-2021	
 
Initial version of the document.
 
	[name] /Sr Statistician [name]/ Statistician

## 2. List of Abbreviations and Definitions of Terms

Abbreviation	Definition
ADE	Adverse Device Effect
AE	Adverse Event
AF	Atrial fibrillation
AT	Atrial Tachycardia
ATP	Anti-tachycardia pacing
CAD	Coronary Artery Disease
CIED	Cardiac Implantable Electronic Device
CIP	Clinical Investigation Plan
CRHF	Cardiac Rhythm and Heart Failure
CRF	Case Report Form
CRT-D	Cardiac Resynchronization Therapy Defibrillator
CRT-P	Cardiac Resynchronization Therapy Pacemaker
CV	Cardiovascular
DBL	DataBase Lock
DD	Device Deficiency
FAS	Full Analysis Set
HF	Heart Failure
HR	Hazard Ratio
ICD	Implantable Cardiac Defibrillator
ICF	Informed Consent Form
ICH	International Conference Harmonization
IPG	Implantable Pulse Generator
IQR	Inter-Quartile Range
ITT	Intention To Treat
LA	Left Atrial
PP	Per Protocol
SADE	Serious Adverse Device Effect
SAE	Serious Adverse Event
SAP	Statistical Analysis Plan
SPR	Statistical Programming Requirements
TIA	Transient Ischemic Attack
USADE	Unanticipated Serious Adverse Device Effect
VHD	Valvular Heart Disease

### 3. Introduction

---

Atrial fibrillation (AF) is the most common sustained cardiac arrhythmia. The prevalence of AF increases with age and, in the elderly population, cardiovascular (CV) risk factors and co-morbidities such as hypertension, diabetes, congestive heart failure, coronary artery disease, valvular heart disease (VHD), and stroke are common. It has also been shown that the prevalence and cost of AF is related to economic growth and an ageing population.

Data from a national atrial fibrillation registry (IHRS-AF) show that Indian AF patients are more than a decade younger than AF patients in the western world. This fact seems to be due to the higher prevalence of hypertension, diabetes, and coronary artery disease (CAD) in the young in India. Also, a subanalysis of the global RealiseAF survey confirms that hypertension is the most common underlying CV condition, followed by ventricular heart disease (VHD), CAD, diabetes, and dyslipidemia. Both the registries report a higher prevalence of persistent/permanent AF, compared to paroxysmal AF, unlike the western AF population.

Anti-tachycardia pacing (ATP) is a therapy delivering series of pacing stimuli that, if delivered at a specific rate, succeed in terminating tachycardias by interrupting the re-entry circuit.

ReactiveATP algorithm allows the device to restart delivering all the ATP therapies, after the entire therapies sequence has unsuccessfully ended, in case of change in arrhythmia rhythm and/or after a programmable time period.

The clinical benefit of Reactive ATP, in terms of reduced incidence of persistent and permanent AF, has been demonstrated in the International, randomized, controlled MINERVA trial. In particular a secondary analysis of that trial showed that ReactiveATP is more effective in case of slow and regular atrial arrhythmias, a condition that can be observed at the onset of the episode or over time.

The evidence of ATP programming is very limited and additional evaluations additional evaluations are required to understand which ATP programming in terms of efficacy is the best in interrupting the arrhythmia and improving battery longevity.

The MANDATE AF Study purpose is to show that a reduced ATP sequence programming is non-inferior to Minerva study ATP programming with respect to time to persistent AF among Indian patients with a Cardiovascular Implantable Electronic Device (CIED).

This Statistical Analysis Plan (SAP) describes methods used to assess the primary and secondary endpoints of this study. The SAP should be read in conjunction with the study protocol and electronic case report forms (eCRF). This version of the plan was developed based on CIP version 1.0 of the 26th February 2019. The SAP has been prepared in agreement with Medtronic internal

procedures and using the CONSORT Statement and International Conference Harmonization (ICH) guidelines E3, E6 and E9 as guidelines.

Due to COVID-19 pandemics that severely impacted the study enrollment, changes in CRHF product portfolio, very minimal Reactive ATP enabled devices available, and change in the local evidence strategy, the operating unit has decided to terminate the study earlier. The Database lock (DBL) is scheduled to occur on September 1st, 2021.

## 4. Study Objectives and Endpoints

---

### 4.1 Objectives

#### 4.1.1 Primary Objective

The primary objective of this study is to show that a reduced ATP sequence programming is non-inferior to Minerva study ATP programming with respect to time to persistent AF among Indian patients with a CIED.

#### 4.1.2 Secondary Objectives

The secondary objectives of the study are:

- to compare the two atrial ATP Programming arms in terms of clinical endpoints reported below, section 4.2.2;
- to evaluate the incidence of persistent AF in patients with sick sinus syndrome compared to the one found in the Minerva trial, and characterize the difference between the European and Indian populations;
- to evaluate the efficacy of atrial ATP therapies as a function of the device type (IPG, ICD, CRT-D, CRT-P), and population characteristics (baseline characteristics, implant indications);
- to describe the incidence of all collected endpoints in the study population.

### 4.2 Endpoints

#### 4.2.1 Primary Endpoint

Time to persistent AF, defined as more than 7 consecutive days of AF, retrieved by using the device AT/AF diagnostics, or time to permanent AF. Time 0 for the time to event calculation is defined as the randomization date or the first day in sinus rhythm after enrollment.

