5.2. Endpoints

The primary endpoint of the study is:

- Time to persistent AF, defined as more than 7 consecutive days of AF, retrieved by using the device AT/AF diagnostics, or time to permanent AF. Time 0 for the time to event calculation is defined as the enrollment date or the first day in sinus rhythm after enrollment. The secondary endpoints include:

- 1. To compare the two atrial ATP Programming arms in terms of clinical endpoints reported below:
 - all-cause death (at the end of 24 months);
 - cardiovascular hospitalization (HF, AF or other), measured as time to first event and annual rate.
 - Annual rate for all-cause hospitalization;
 - AT/AF burden metrics, measured in terms of time to first event (daily burden ≥ 1 day, ≥ 2 days, ≥ 30 days) or the ratio between time in AT/AF and the observation period;
 - number of successful and unsuccessful treated AT/AF episodes out of detected episodes;
 - number of delivered therapies per episode;
 - number of ATP sequences;
 - stroke, TIA or other thromboembolic events;
 - LA diameter (where available);
 - percentage of patients treated by anticoagulation therapy according management guideline;
 - electrical or pharmacological cardioversions measured in terms of time to first event and annual rate;
 - biventricular pacing percentage (in CRT-P /CRT-D patients);
- 2. Composite endpoint made of death, cardiovascular hospitalizations, stroke, TIA or other thromboembolic events.
- 3. To evaluate the incidence of persistent AF in patients with sick sinus syndrome compared to the one found in the Minerva trial, and characterize the difference between the European and Indian populations.
- 4. To evaluate the efficacy of atrial ATP therapies as a function of the device type (IPG, ICD, CRT-D, CRT-P), and population characteristics (baseline characteristics, implant indications).

6. Study Design

This multi-center randomized study analyses patients implanted with a Medtronic cardiac implantable device with an atrial lead and equipped with atrial ATP therapies. The patients should have been implanted for no more than 18 months prior to enrollment.

Patients will be randomized into two groups:

- 1) an interventional arm including patients with a conservative atrial ATP therapies programming setting;
- 2) a control arm including patients with the same atrial ATP therapies programming setting adopted in the Minerva Trial.

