9.6. Assessment of Efficacy

Device data containing information about AT/AF episodes occurrence and duration will be collected every six months for all the enrolled patients, and every 3 months from patients who are on remote monitoring with a MyCareLink monitor. The list of arrhythmic episodes reported in the episode log and the cardiac Compass trends will be used to identify the following occurrences among the whole study population during the entire study period:

- AT/AF incidence and episodes duration;
- Incidence of persistent AF (defined as more than 7 continuous days of AF);
- Biventricular pacing percentage in CRTP/CRTD patients.

The definition of permanent AF will be based on the physicians' decision that nothing further can be done to cardiovert the patient.

All these data will be inserted in the study eCRFs, in addition to the save to disk collected during the in-office follow-up visits.

The primary endpoint will be measured in terms of time to persistent AF in the two study groups.

The secondary endpoints will be measured by using device and MyCareLink data, and hospital's clinical records reporting information regarding hospitalizations, deaths, cardioversions, AT/AF episodes incidence and daily burden, biventricular pacing percentage, occurrence of thromboembolic events and echocardiographic parameters.

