### **7.2.2 Derived Variables**

Variables to evaluate the primary endpoint, as well as daily AF burden metrics, number of successful and unsuccessful treated AT/AF episodes out of detected episodes, number of delivered therapies per episode, and number of ATP sequences will be derived from the device datasets and will be described in detail in the SPR (ref).

The exposure time (months) for the time to first persistent AF will be computed from the date of randomization to the date of the last device save to disc for patients without persistent AF recurrence or to the date of first recurrence of persistent AF recurrence otherwise  $[(\text{data end} - \text{data in})/30.4]$ .

Variables to evaluate secondary endpoints as all-cause death, cardiovascular hospitalization (HF, AF or other), stroke, TIA or other thromboembolic events and annual rate for all-cause hospitalization will be derived from the adverse event dataset and will be described in detail in the SPR (ref).

The exposure time (months) for the secondary endpoints will be computed from the date of randomization to the date of the notice (follow-up visit or adverse event) for patients without events or to the date of the specific event otherwise  $[(\text{data end} - \text{data in})/30.4]$ .

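### The SAP gives the primary endpoint conflicting start, end and censoring dates, so a patient randomised during AF, or declared in permanent AF, can be classified in more than one way

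*SAP*

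**What the plan says.** **Start.** SAP 4.2.1: "Time 0 for the time to event calculation is defined as the randomization date or the first day in sinus rhythm after enrollment". Protocol 5.2: "Time 0 for the time to event calculation is defined as the enrollment date or the first day in sinus rhythm after enrollment"; SAP 7.9.1 repeats that protocol sentence. SAP 7.2.2 has no alternative: "The exposure time (months) for the time to first persistent AF will be computed from the date of randomization". Protocol 13.2.9 offers the sinus-rhythm origin only to patients with an event and starts all others at enrolment.

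**End.** The endpoint in SAP 4.2.1 and 7.9.1 covers persistent AF "retrieved by using the device AT/AF diagnostics, or time to permanent AF". Protocol 9.6 defines permanent AF by the physician's "decision that nothing further can be done to cardiovert the patient", and then sends the efficacy data to the eCRF. SAP 7.2.2 says: "Variables to evaluate the primary endpoint, as well as daily AF burden metrics" and other items "and number of ATP sequences will be derived from the device datasets". It stops the clock at the last save to disc, "or to the date of first recurrence of persistent AF recurrence otherwise". Permanent AF is not mentioned there.

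**Censoring.** SAP 7.2.2 uses the last device save. SAP 7.4 uses the last available contact date for patients lost to follow-up.

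**Who is analysed.** Protocol 8.4 excludes permanent AF and AF runs of more than 7 consecutive days ending on the day of enrolment. SAP 7.1.3 analyses the FAS, which does not require a day in sinus rhythm.

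**The concern.** A patient in AF for 7 days or less at the baseline visit is eligible. If that run passes 7 days before any sinus-rhythm day, the SAP does not settle whether an event has occurred, or when. A sinus-rhythm origin also depends on something that happens after randomisation and that the assigned programming may influence. Under Protocol 13.2.9 the origin would depend on the outcome itself.

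Read literally, SAP 7.2.2 censors a patient declared in permanent AF who has no device-recorded persistent run. SAP 7.1.3 says that device interrogation compliance fell far short of plan, so such gaps are possible.

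At stake is whether there is one primary-endpoint table or several. SAP 7.12 leaves the final decision on endpoint evaluation until the data have been collected and assessed, so an unsettled clock could be settled with outcomes in view.

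**Working it through.** The plan gives no figure for this point, and the sample size of 758 does not enter into it. The check applies the written rules to assumed rhythm histories and then sizes one reclassification.

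**1. Histories.** Assume day 0 = enrolment = randomisation. The event falls on the 8th consecutive AF day, and only AF days from day 0 count unless stated. Months = days/30.4, as in SAP 7.2.2.

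| History | Clock from randomisation (7.2.2) | Clock from first sinus-rhythm day |
|---|---|---|
| AF days 0–19, then sinus rhythm | Event day 7: 7/30.4 = 0.23 month | No event |
| AF days 0–19, sinus rhythm days 20–119, AF from day 120 | Event day 7: 0.23 month | Event day 127: 127 − 20 = 107 days, 107/30.4 = 3.52 months |
| AF throughout | Event day 7: 0.23 month | No time 0, yet the patient is in the FAS |
| 5 AF days before enrolment, AF days 0–2, then sinus rhythm | Event day 2 if earlier AF days count (5 + 3 = 8); otherwise none | No event |

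The fourth row is eligible: at enrolment the run is 5 + 1 = 6 days. No section says whether AF days before randomisation count towards the 7.

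**2. Outcome-dependent origin (Protocol 13.2.9).** Take two patients who both first reach sinus rhythm on day 20. One has an event on day 127 and may be given 127 − 20 = 107 days. The other is censored on day 127 and is given 127 days. The same observed span yields different times because of the outcome.

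**3. Size of one reclassification.** SAP 6 gives 37 patients in the interventional arm and 38 in the control arm.
- Patient removed for lack of a time 0: k/n − (k − 1)/(n − 1), with k events in an arm of n. For n = 37: k = 1 gives 2.70 points; k = 6 gives 16.22 − 13.89 = 2.33. For n = 38: k = 1 gives 2.63; k = 6 gives 15.79 − 13.51 = 2.28.
- Patient kept but counted as event-free: 1/37 = 2.70 points or 1/38 = 2.63 points, for any k.

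**4. How many events to expect.** Apply the planned control-arm survival of 85% at 24 months to both arms, with a constant hazard: −ln(0.85)/24 = 0.00677 per month. Expected events are n × (1 − exp(−0.00677t)). Actual follow-up is not given, so t is an assumption.

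| Assumed mean follow-up t (months) | n = 37 | n = 38 |
|---|---|---|
| 6 | 1.47 | 1.51 |
| 12 | 2.89 | 2.97 |
| 24 | 5.55 | 5.70 |

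One event would be a visible share of an arm's total.

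**5. Timing alone.** If no event precedes the first sinus-rhythm day, the origin moves by at most 7 days (7/30.4 = 0.23 month). At the same hazard this shifts the survival estimate by 0.150 point at 6 months, 0.144 at 12 and 0.132 at 24, even if every patient entered in AF. The bound is not general: in the second history the recorded time moves from 0.23 to 3.52 months.

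**The case against.** - **The data exist.** A reader might infer that the study has no usable source for permanent AF. The documents do not support that. Protocol 9.6 sends these data to the eCRF, the SAP is to be read with the protocol and eCRF, and SAP 7.2.2 defers detail to a programming document that is not available here. What stands is narrower: SAP 7.2.2 names neither the source nor the date, and a programming document would not remove the contradictions within the SAP.
- **Few patients may be affected.** SAP 7.1.3 expects no significant difference in size between the PP and ITT sets. By definition these differ only in the sinus-rhythm day, so the SAP expects few patients without one. This is an expectation tied to low enrolment, not a count. It also does not cover patients who return to sinus rhythm after an early event.
- **The FAS did not create the gap.** The protocol's ITT set never required a sinus-rhythm day either. That is correct; the gap arises from the unexplained alternative in time 0.
- **The intent can be guessed, and a smaller repair exists.** The PP definition suggests enrolment for patients in sinus rhythm and the first sinus-rhythm day otherwise. Writing that down, with a rule for patients who have no such day, would remove the ambiguity. It would still leave an origin that follows randomisation and may be affected by it.
- **Nothing is tested.** No hypothesis test or hazard ratio is planned, and Kaplan-Meier output appears only if patient and event numbers are adequate. This stands and limits the severity.

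**Conclusion.** The SAP is wrong as written on this point, with minor to moderate consequence. Sections 4.2.1, 7.2.2 and 7.9.1 do not give one time 0. Section 7.2.2 read literally censors part of the defined endpoint, and 7.2.2 and 7.4 censor patients lost to follow-up at different dates. The choice between enrolment and randomisation probably matters little, because Protocol 9.1.1 places randomisation at the baseline visit. The sinus-rhythm alternative and the handling of permanent AF matter more.

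The figure of about 2.3 to 2.7 points is for one hypothetical reclassified patient in an arm of 37 or 38 with 1 to 6 events. It is not an estimate of the actual effect. The number affected and the direction are unknown, and the number may be zero. A reader might infer that events have been lost or that one arm is favoured; the documents support neither.

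**What to change.** Settle the following before database lock (the SAP is dated 27 August 2021 and lock is scheduled for 1 September 2021):

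1. Use the randomisation date as time 0 for every FAS patient, with or without an event, in SAP 4.2.1, 7.2.2 and 7.9.1. Record this in SAP 7.12 as a change from Protocol 5.2 and 13.2.9, with the reason.
2. In SAP 7.2.2, make the event date the earlier of device-detected persistent AF and the eCRF date of the permanent-AF decision.
3. Use one censoring rule for this endpoint in SAP 7.2.2 and 7.4: the last device save. List permanent-AF decisions dated after the last save separately by arm, so that events and exposure cover the same window.
4. Count towards the 7 days only AF days on or after randomisation, in line with time 0.
5. Keep the sinus-rhythm origin as a labelled sensitivity analysis. Report by arm how many patients were in AF at randomisation and how many had the event before any sinus-rhythm day.

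The cost is a few sentences in the SAP and matching lines in the programming document. No new data are needed, provided that the eCRF dates the permanent-AF decision. The downsides are a recorded departure from the protocol wording, possibly a few very early events, and some late permanent-AF decisions that are listed rather than counted. The sensitivity analysis and the listings by arm would make these visible.
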